1.1 Background

Type 2 diabetes is a cardiometabolic disorder with associated vascular disease associated with half a decade of life years lost¹ or a decade and half among those with atherosclerotic cardiovascular disease (ASCVD).² Despite significant improvements in outcomes, mortality and morbidity remains higher among those with type 2 diabetes vs those without. A global approach starting with lifestyle and pharmacotherapy to address multiple risk factors is required to reduce the burden of disease. Observational data supports the notion that control of multiple risk factors attenuates the residual risk especially among younger subjects.^{3 4}

Broadly, complications of type 2 diabetes can be broken down into those that affect the macrovascular system (myocardial infarction, stroke, peripheral arterial disease) and those that affect the microvascular system (chronic kidney disease, retinopathy, neuropathy). The former requires control of multiple factors that affect cardiovascular disease such as lipid lowering, blood pressure control, and smoking cessation (among others). The latter is more closely related to long-term glycaemic control in particular, but potentially other factors such as BP control and use of specific therapies aimed at end organ preservation (e.g., RAS blockade, SGLT2 inhibitors).

Practice nurses (PNs) in primary care spend significant time in consultations with patients about managing their type 2 diabetes. Group consultations have been identified as an opportunity to improve outcomes and access, whilst engaging patients in a different way that offers the potential to provide a more social and less medical model of planned care.⁵ Experience in other parts of England suggested that it could also improve staff experience by reducing repetition and creating more time to care and support patients.⁵ Group consultations also have a strong evidence base of impact in type 2 diabetes, with seven randomised controlled trials showing improvements in HbA1c compared to one-to-one care.⁶

1.2 Study Rationale

As the prevalence of Type 2 Diabetes Mellitus (T2DM) grows the burden on healthcare is increasing in the form of additional consultations, hospital outpatient visits, death and disability. T2DM represents a large part of the disease and cost burden of healthcare in North West London (NWL) to the value of £600m annually. Patients with T2DM constitute over 40% of all NWL admissions, with complications of type 2 diabetes representing a significant factor in the morbidity and cost associated with this chronic disease. To this end, there is an urgent need for healthcare professionals to provide the same or better care without increasing healthcare expenditure. Digital interventions/ healthcare solutions may provide an opportunity to achieve these goals.

The Type 2 Diabetes Exemplar Programme has designed the Fresh Start service for use in primary care to demonstrate how real-world data and technology can improve health outcomes for T2DM patients. Fresh Start has been designed by the Discover-NOW Health Data Research Hub in a cross-industry collaboration between North West London CCGs, NHSX, AstraZeneca, Imperial College Health Partners and Huma. Fresh Start is offered to patients at high risk of developing complications from T2DM and combines video group consultations, a remote monitoring solution, and educational content.

Fresh Start seeks to support population stratification and strengthen population health management by providing better-tailored services and proactive interventions, particularly among population groups more at risk of the adverse impacts of COVID-19. Mortality risk from COVID-19 is approximately 25% higher in patients with T2DM and shielding has resulted in reduced primary care appointments for patients with T2DM. This has created an immediate need for primary care to adapt and provide remote care pathways to patients. Digital-first remote pathways could make care more accessible while finding time and cost efficiencies. By combining remote monitoring and video group consultations, we can inform the patient-clinician conversation making remote care in group settings safer, efficient and more personalised.

It is our opinion that generating credible evidence for digital health solutions remains an industry-wide challenge, hindering widespread adoption, and that traditional approaches present limitations for researchers to create evidence. Evaluation of digital health solutions has also been identified as requiring improvement and has been cited as a major obstacle for wider adoption.^{7 8} This study will use pragmatic methods to evaluate Fresh Start, with a view to support successful adoption of Fresh Start in primary care practices in the UK.

2. Study aims and objectives

The aim of T2DEx is to assess the feasibility, usability, acceptability, cost-effectiveness and safety of a remote care service (“Fresh Start”) in primary care for people with ‘high risk’ or ‘very high risk’ Type 2 Diabetes in North West London.

The study will assess patient and clinician experience metrics, the feasibility of implementation including uptake and patient/physician acceptability for data collection procedures, and the resources needed to manage and implement Fresh Start. The study will also assess the impact of Fresh Start on clinical outcome measures (e.g., HbA1c, risk factor control, time at goal).

The results of this may support continuation of Fresh Start. A follow-up study with a larger number of participants and longer duration would be required to assess a statistically significant impact on secondary objectives.

Primary objectives:

1. To assess the **feasibility of uptake** amongst people with 'high risk' or 'very high risk' type 2 diabetes.
2. To assess the **usability** of Fresh Start amongst **people with 'high risk' or 'very high risk' type 2 diabetes**.
3. To assess the **usability** of Fresh Start amongst **HCPs**.
4. To assess the **acceptability** of Fresh Start amongst **people with 'high risk' or 'very high risk' type 2 diabetes**.
5. To assess the **acceptability** of Fresh Start amongst **HCPs**.
6. To assess the **cost-effectiveness** of delivering Fresh Start.

Secondary objectives (**EXPLORATORY** only and will not be demonstrated to a level of statistical significance):

1. To assess the **safety** of **Fresh Start**.
2. To assess the **impact of Fresh Start on clinical outcomes**.

3. Study design and methods

3.1 Design

An experimental feasibility study with a pre-test/post-test design using a matched control.

3.2 Study population

In response to the public health emergency posed by COVID-19, NHS England and NHS Improvement (London) are supporting clinicians to identify patients who are at the higher risk of adverse outcomes (based on available evidence) and prioritise the allocation of existing resources to these patients.

The study population therefore includes people with 'high risk' and 'very high risk' type 2 diabetes (see 'Inclusion criteria'), as defined by guidance for primary care from NHS England and NHS Improvement (London), entitled *Primary Care: Identification, risk stratification and interventions for patients at an increased risk*.

3.3 Sample size

The study will seek to collect and analyse data from a minimum of 300 participants to Fresh Start. With an estimated enrolment rate of 20%, 1,500 eligible patients will need to be identified and we will be able to estimate this rate within a 95% confidence interval of +/-3%, accounting for variance inflation due to clustering with the assumption of 10 GP practices and Intraclass Correlation Coefficient (ICC) of 0.05.

The study's secondary objectives are exploratory only and will not be demonstrated to a level of statistical significance in this study.

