7.5. Primary Analysis Methodology

7.5.1. Feasibility of uptake amongst people with ‘high risk’ or ‘very high risk’ type 2 diabetes

For both definitions of comparative measures as defined in 6.2.1, frequencies of each category will be presented with proportions established as percentages presented to 1 decimal place (dp)

- Patients enrolled vs patients initially offered device
- Patients collecting Fresh Start data vs patients enrolled.

7.5.2. Usability of Fresh Start amongst people with ‘high risk’ or ‘very high risk’ type 2 diabetes.

Summary statistics denoting mean, sd, median, 1st/3rd quartiles, and minimum/maximum events per patient and per patient per unit time (day/week as appropriate) will be derived. Results will be presented as mean (SD) for normally distributed data and median [Q1-Q3] for skewed:

- Number of **Video Group Consultations (VGC)** attended per patient
- Number of **Blood Glucose measurements** recorded per patient within HUMA
- Number of **Blood Pressure measurements** recorded per patient within HUMA
- Number of **Weight measurements** recorded per patient within HUMA
- Number of **Diabetes Distress Score (DDS)** measurements recorded per patient within HUMA

For Fresh Start emails, the following frequencies will be presented, any additional information may also be presented:

- Number of patients that interacted with all emails

- Number of patients that interacted with no emails
- Interactions per email (click rates)

7.5.3. Acceptability of Fresh Start amongst people with 'high risk' or 'very high risk' type 2 diabetes.

Interviews are to be carried out by members of the research team from the Institute of Global Health Innovation (IGHI) at Imperial College London and will form part of a qualitative analysis. Interviews conducted with participants will be analysed using NVivo, where responses will undergo thematic analysis using an inductive approach to derive key themes.

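### The stated 95% precision of ±3 points for the enrolment rate does not follow from the plan's own inputs, which give about ±5.9 points; ±3 points is one clustered standard error

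*Protocol*

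**What the plan says.** Protocol 3.3 sets out to "collect and analyse data from a minimum of 300 participants to Fresh Start". It continues: "With an estimated enrolment rate of 20%, 1,500 eligible patients will need to be identified". It then gives the precision this delivers: "we will be able to estimate this rate within a 95% confidence interval of +/-3%, accounting for variance inflation due to clustering". The clustering inputs are 10 GP practices and an "Intraclass Correlation Coefficient (ICC) of 0.05". SAP 5.5 carries the same statement. Neither document shows the design effect, the cluster size or the formula.

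The rate concerned is patients enrolled out of patients offered the service (Protocol 3.6; SAP 6.2.1). For its analysis, SAP 7.5.1 says that "frequencies of each category will be presented with proportions established as percentages presented to 1 decimal place (dp"). SAP 7.2 likewise lists only a frequency and a percentage for this outcome. Neither section plans a confidence interval for it.

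**The concern.** Every input needed to reproduce the figure is given, and the text says clustering has been allowed for. With only 10 clusters of about 150 patients each, even a modest ICC inflates the variance heavily, so ±3 points looked too narrow.

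Feasibility of uptake is the first primary objective, and this is the only quantitative statement of what the sample size will achieve. Protocol section 2 says the results may support continuing the service and that a larger follow-up study would be needed. Someone planning that study from an observed 20% would take the plausible range as 17% to 23%, when the design supports roughly 14% to 26%. Because the uptake table will show a percentage to one decimal place with no interval, nothing in the reported results would correct that impression.

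**Working it through.** **Inputs** (Protocol 3.3, repeated in SAP 5.5): rate p = 0.20; patients n = 1,500; practices k = 10; ICC = 0.05; 95% confidence, taken as two-sided, so z = 1.96.

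**Patient numbers.** 300 / 0.20 = 1,500. This reproduces.

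**Precision as described**

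1. Mean cluster size: m = 1,500 / 10 = 150.
2. Design effect: 1 + (m − 1) × ICC = 1 + 149 × 0.05 = 8.45.
3. Effective sample size: 1,500 / 8.45 = 177.5.
4. Standard error: √(0.20 × 0.80 × 8.45 / 1,500) = 0.0300, or 3.00 points.
5. 95% half-width: 1.96 × 0.0300 = 0.0588, or 5.9 points (14.1% to 25.9%).
6. With t on 10 − 1 = 9 degrees of freedom: 0.0679, or 6.8 points.

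The stated ±3% matches step 4, not step 5. Under the normal approximation, an interval of ±1 standard error covers about 68%.

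**Can another reading give ±3%?**

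| Reading | Half-width (points) |
|---|---|
| No clustering | 2.02 |
| Design effect 1 + m × ICC | 5.90 |
| Wilson interval on effective n (14.8% to 26.5%) | 5.86 |
| 90%, or one-sided 95%, multiplier | 4.94 |
| 80% multiplier | 3.85 |
| 30 enrolled per practice, n = 300 (design effect 2.45) | 7.09 |
| 30 enrolled per practice, n = 1,500 (design effect 2.45) | 3.17 |

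Only the last rounds to 3. It takes the cluster size from the enrolled patients (300 / 10) and the denominator from all 1,500 identified. The rate is measured over everyone offered the service, about 150 per practice, so that route would also be an error.

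**What ±3 points would require**

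- Design effect allowed: (0.03 / 1.96)² × 1,500 / 0.16 = 2.196.
- With 10 practices: ICC = (2.196 − 1) / 149 = 0.008.
- With ICC 0.05: m = 1 + 1.196 / 0.05 = 24.9, so about 1,500 / 24.9 = 60 practices.
- Lower limit with 10 practices at ICC 0.05, as the number of patients grows without bound: 1.96 × √(0.16 × 0.05 / 10) = 0.0554, or 5.5 points.

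**Consequence for planning.** To enrol 300, rates of 23% and 17% mean approaching 300 / 0.23 ≈ 1,304 to 300 / 0.17 ≈ 1,765 patients. Rates of 25.9% and 14.1% mean 300 / 0.259 ≈ 1,158 to 300 / 0.141 ≈ 2,128.

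**The case against.** The arithmetic is not in dispute. The case on the other side concerns its cause and its weight.

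- **The cause is not documented.** No formula is shown, so an omitted 1.96 is an inference, and the 3.17-point route is a possible alternative. This stands. It does not rescue the figure, because both explanations are errors.
- **Precision may not have set the size.** The text starts from a minimum of 300 participants, derives 1,500 from it, and then states the precision obtained. This stands too: the plan does not say that 300 or 1,500 was chosen to reach ±3%. It remains the only precision claim made for the sample.
- **No decision turns on it.** This is a feasibility study with descriptive primary outcomes and no uptake threshold or progression criterion, so no pass/fail result changes. True, but estimating the rate is then the purpose of the exercise, and its stated precision is wrong by a factor of about two.
- **The missing interval in SAP 7.5.1 is a reporting gap, not an arithmetic error.** Fair. It is a separate and secondary matter. Still, the SAP allows for clustering by practice in its appointment, cost and clinical outcome models but not for the one rate whose precision was worked out with clustering in mind.
- **The t-based figure depends on a choice of multiplier that the plan does not make.** Correct. The direct correction of the stated claim is 5.9; 6.8 shows the further effect of having only 10 clusters.

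**Conclusion.** The concern holds. From the plan's own inputs, the 95% half-width for the enrolment rate is about ±5.9 percentage points, or ±6.8 with t on 9 degrees of freedom. The stated ±3% equals one clustered standard error and cannot be reached with 10 practices at an ICC of 0.05.

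The result assumes equal practice sizes and that all 1,500 identified patients are offered the service. Unequal practice sizes would widen the interval, and so would fewer patients offered the service. It also takes the plan's 10 practices and ICC of 0.05 as given; a materially smaller ICC would narrow the interval. The targets of 300 enrolled and 1,500 identified are consistent with each other and are not affected.

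**What to change.** - **Protocol 3.3 and SAP 5.5:** restate the precision as about ±5.9 percentage points (about ±6.8 using t with 9 degrees of freedom) for 1,500 patients in 10 practices at ICC 0.05. Show the cluster size of 150 and the design effect of 8.45 so that the figure can be checked.
- **SAP 7.5.1, with the matching row of SAP 7.2:** report the enrolment percentage with a 95% confidence interval that allows for clustering by practice, and name the method.

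The cost is one corrected figure in two documents and one extra interval in the uptake table. The number of patients and practices need not change. The stated precision becomes less favourable.

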3.4 The Fresh Start service

This 12-week service has been designed to optimise patient care based on pro-active identification and prioritisation of clinical risk based on health, socioeconomic and demographic factors.

Fresh Start seeks to assess whether alternative methods of healthcare delivery for people with high-risk or very high risk T2DM are safe, scalable, and cost-effective. Fresh Start has been co-designed with people with type 2 diabetes, healthcare professionals (GPs, specialists, nurses, podiatrists, dietitians) and commissioners from Collaboration Of North West London Clinical Commissioning Groups (NWL CCGs).

The North West London Diabetes Clinical Reference Group (CRG) reviewed and provided feedback on Fresh Start's design. The CRG comprised of three GPs, three endocrinologists, three vascular surgeons, two specialist podiatrists, two diabetes nurse specialists, one district nursing lead, one infection control lead, two commissioners/quality improvement leads and one psychiatrist.

Fresh Start will support delivery of the new Integrated Care System (ICS) and Primary Care Network (PCN) models currently being rolled-out across the NHS.

The Fresh Start service and SOPs have been specifically designed to enable a new model of care as part of the NHS Long Term Plan.

Individual primary care practices play a central role in service delivery. GPs, nursing staff and administrative staff from primary care practices have advised how best to adopt Fresh Start into the primary care clinical workflow and have helped to develop standard operating procedure (SOP) documentation to support participating practices.

The 12-week service comprises the following elements (overview provided at Appendix 1):

- I. **Proactive risk stratification.** An electronic patient record (EPR) based risk stratification search is run at primary care practice level to identify T2DM patients at high risk of cardiovascular complications who may benefit from and be eligible for Fresh Start.
- II. **Video Group Consultations (VGC).** Each patient is invited to attend a total of three VGCs during the 12-weeks lasting approximately one hour and 15 minutes each. Each session is facilitated by a Practice Nurse (PN) and consists of 6-10 people with T2DM. The self-reported Huma app (see below) and patient EPR data are used to populate a "Discussion Dashboard" which is used in each VGC to facilitate discussion. During the first VGC session, patient goals are discussed and adjusted in a group setting with topics relevant to their condition covered by the PN. Between each VGC session, patients spend time working on their goals and continuing to enter self-reported metrics into the Huma app. During the second and third VGC sessions, each patient is discussed, along with their performance against agreed goals. The PN also uses pre-prepared content to discuss topics relevant to managing type 2 diabetes (e.g., staying motivated, low carb diets).
- III. **Fresh Start educational email campaigns.** Each patient is signed up to a series of educational email campaigns to complement the VGC sessions and provide broader

education around type 2 diabetes management. Patients receive two emails per week during the 12-week service on a variety of topics.

- IV. **Clinical protocols.** A series of best-practice CRG approved clinical protocols are in place to be triggered based on thresholds and values captured via the Huma app and as part of the VGC sessions. Protocol examples include medications review, foot care, renal, and mental health.
- V. **Digital remote patient monitoring** using blood pressure and blood sugar devices in combination with a smartphone application ('the Huma app'). Participants are provided with home monitoring devices and download the Huma app. Participants are shown how to use the devices, how to input measurements into a smart phone and how to set personal goals. Data recorded via the Huma app is self-reported and includes activity data, diet information, blood glucose measurements, blood pressure measurements, weight, and the Diabetes Distress Scale (a self-reported questionnaire used to measure distress related to living with diabetes). A Health Care Assistant (HCA) observes these data via a Huma clinician dashboard that complements the Huma app. The HCA presents these data in combination with relevant EPR data to the PN for review ahead of each VGC appointment.
- VI. **One-to-one routine patient review.** At the end of the 12-weeks participants are invited to a one-to-one review session with their primary care practice. The patient's progress over the 12-week service is reviewed and a decision is made whether to discharge patient, repeat them for another 12 weeks on Fresh Start, or escalate them to MDT.

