3.11 Data analysis

The research team will not have access to any personal or identifiable patient data as part of the project. Data will be de-identified before being transferred to WSIC's de-identified data (DID) environment and made available to approved researchers. Any data extracted from the secure environment after analysis by the research team will be at an aggregate level only.

All outcomes will be reported using descriptive statistics with tables and graphical presentations of findings. Continuous variables will be presented as means and standard deviations if normally distributed, and as medians and inter-quartile ranges for skewed data, whilst categorical variables will be presented as frequencies and percentages.

To assess the pre-test/post-test change on clinical outcomes the appropriate generalized mixed model approach will be used to account for repeated measurements and clustering of GP practices and including important covariates in the model.

To create a matched control group from NWL's WSIC database, a 1:1 propensity score matching (PSM) analysis will be performed using age, gender, risk category, geographical proximity and social deprivation index as matching variables. R statistical software will be used for estimating PS by logistic regression and for balance and sensitivity checks.

Comparisons with the control group for clinical outcomes will be exploratory and differences with 95% CI will be reported using the appropriate generalized mixed model.

Interviews conducted with participants and healthcare professionals will be analysed using NVivo, where responses will undergo thematic analysis using an inductive approach to derive key themes.

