7.1.2. Propensity Score Matching

For the primary cost-benefit comparison and secondary safety and efficacy comparisons, study data will be compared against a matched-control group established via propensity score matching. This is achieved by deriving a propensity score for each enrolled patient based on the following characteristics:

- Age
- Gender
- Geographical proximity
- Social deprivation index (by practice)

- Ethnicity

Using the above categories, taking 'arm' as the dependent variable, logistic regression using a generalised logit model will be used to generate the estimated propensity scores. Scores are also applied to a control 'arm' taken from the WSIC database as section 5.2.2 with everyone in the matched control identified within one month of the index case. The scores are then used to 'pair-up' patients within both groups, patients will be matched on a 1:1 basis without replacement.

Scores are to be calculated using PSOCORE in STATA. Matching is to be carried out using PSMATCH2 (or a suitable alternative). Balancing on matching variables is to be checked once matching is completed using PSTEST. If any variable is found to be unbalanced the matching is repeated, either adjusting the matching method or caliper used.

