7.5.5. Cost-effectiveness of delivering Fresh Start

From the three sets of data established in 6.2.6, cost-effectiveness of Fresh Start is to be assessed via the following:

- Number of primary care appointments per patient - as entered in study dataset over the 12-week assessment period

Summary statistics will be derived for mean, sd, median, 1st/3rd quartiles, and minimum/maximum. Results will be presented as mean (SD) for normally distributed data and median [Q1-Q3] for skewed.

To assess for differences in frequency of appointments per patient between Fresh Start and the matched control group, a Poisson-based mixed effects model with covariates for sex, age, social deprivation index will be used allowing for clustering by GP practice.

- Cost per appointment per patient - as entered in study dataset

Summary statistics will be derived for mean, sd, median, 1st/3rd quartiles, and minimum/maximum. Results will be presented as mean (SD) for normally distributed data and median [Q1-Q3] for skewed.

To assess for differences in cost of appointments per patient between Fresh Start and the matched control group, a mixed-model approach with covariates for sex, age, social deprivation index will be used allowing for clustering by GP practice.

- Cost of equipment per patient

Imperial Clinical Trials Unit	SUB-STUDY SAP TEMPLATE – SUB-ANALYSES AND OBSERVATIONAL STUDIES	SOP_TEM_BS002
-------------------------------	---	---------------

Costs per patient will be estimated using the figures provided in section 6.2.6.1. Once established, summary statistics will be derived for mean, sd, median, 1st/3rd quartiles, and minimum/maximum. Results will be presented as mean (SD) for normally distributed data and median [Q1-Q3] for skewed

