7.6. Secondary Analysis Methodology

7.6.1. Safety of Fresh Start

From the safety parameters established in 6.3.1, safety of Fresh Start is to be assessed via the following over 6 months:

- Number of deaths

Number of deaths is to be presented by frequency per group.

- Number of emergency department admissions

Number of patients with emergency admissions is to be presented by frequency per group

- Number of hospital admissions

Frequency of events per patient is to be presented in a frequency table by treatment group with percentages to 1 dp.

Number of patients with hospital admissions is to be presented by frequency per group

Statistical comparison of safety will consist of a composite outcome, including all three events listed above. Number of patients with a safety event occurring is to be presented by frequency per group with difference in number of patients presented with a 95% CI.

7.6.2. Impact of Fresh Start on clinical outcomes.

From the clinical outcome parameters established in 6.3.2, potential efficacy of Fresh Start is to be assessed via the following

- **HbA1c, at baseline, 12-week and at 6 months**
- **Lipids, at baseline, 12-week and at 6 months**
- **Weight, at baseline, 12-week and at 6 months**

Tables displaying summary statistics will be produced displaying mean, SD, median, minimum & maximum at timepoints BL, W12 & M6

Within-group change from baseline at 12 weeks will be assessed via a mixed-effects model taking values at 12-weeks as the dependant variable and adjusting for covariates; baseline, sex, age, social deprivation index and allowing for clustering by GP Practice

Between-group differences in change from baseline at 12 weeks will be analysed using a similar mixed-effects model including an additional parameter for treatment effect and again adjusting for covariates; baseline, sex, age, social deprivation index and allowing for clustering by GP Practice

Further analysis will take place once long-term (6-month) follow-up is completed using an adjusted version of the above models containing additional terms for visit and visit*treatment interaction.

- **Diabetes Distress Scale score (DDS), as recorded within HUMA once monthly across the 12-week assessment period and also at 6 months**

Summary statistics displaying mean, SD, median, minimum & maximum DDS will be produced at for first reading and last reading.

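### Fresh Start is delivered in video groups of 6-10, but the comparison models allow for GP practice only, so intervals can be too narrow if controls share practices with Fresh Start patients

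*Protocol*

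**What the plan says.** Group sessions are a core component of the service. In Protocol 3.4, "Each patient is invited to attend a total of three VGCs during the 12-weeks". On the sessions themselves: "Each session is facilitated by a Practice Nurse (PN) and consists of 6-10 people with T2DM". In the first session, "patient goals are discussed and adjusted in a group setting with topics relevant to their condition covered by the PN". Later sessions review each patient's progress in front of the group. SAP 5.2.1 repeats this description.

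Controls are untreated patients drawn from the WSIC database (Protocol 3.5, SAP 5.2.2). In SAP 7.1.2, "patients will be matched on a 1:1 basis without replacement", on a propensity score that includes geographical proximity and practice-level deprivation.

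The comparison models name one level of clustering between patients:

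- Appointments (SAP 7.5.5): "a Poisson-based mixed effects model with covariates for sex, age, social deprivation index will be used allowing for clustering by GP practice". The appointment-cost model has the same covariates and the same cluster.
- HbA1c, lipids and weight (SAP 7.6.2): covariates are "baseline, sex, age, social deprivation index and allowing for clustering by GP Practice", in the within-group and the between-group model alike.
- Protocol 3.11 says the mixed models for pre/post change will "account for repeated measurements and clustering of GP practices and including important covariates in the model". Repeated measurement is a level within the patient, not a group level.

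Neither document has a VGC-group or facilitator term, or a plan to record group membership for analysis.

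**The concern.** Patients who share a session share a facilitator, a date, a discussion and each other. Their outcomes may be correlated beyond what their practice explains, and this extra correlation exists only in the Fresh Start arm. A practice intercept common to both arms cannot represent variance present in one arm only. A model without the group level then treats Fresh Start patients as more independent than they are, and the interval for the difference from control is too short.

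At stake are the intervals for appointments and appointment cost, which belong to a primary objective and are compared with control, and those for HbA1c, lipids and weight, which are exploratory. The results may support continuation of the service, and a larger study is foreseen (Protocol section 2). An estimate of group-level variance would help to design that study, but it cannot be obtained if membership is not recorded.

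**Working it through.** **The plan's own figure.** The plan gives no precision for these comparisons. Its only figure that includes clustering is ±3% for the enrolment rate (Protocol 3.3, SAP 5.5), which concerns practices and not groups. Its inputs give a design effect of 1 + (150 − 1) × 0.05 = 8.45 and a half-width of 1.96 × √(0.2 × 0.8 / 1,500 × 8.45) = ±5.9%. That mismatch is a separate matter and does not bear on this point.

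**Inputs from the documents.** 300 Fresh Start patients ("The study will seek to collect and analyse data from a minimum of 300 participants to Fresh Start"), 10 practices assumed, groups of 6-10, 1:1 matching. So 300 / 10 = 30 patients per practice, in 30 / 10 = 3 to 30 / 6 = 5 groups.

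**Inputs assumed.** VGC-group ICC ρ of 0.02, 0.05 or 0.10. Practice ICC for the outcome 0.05; the plan gives this value for the enrolment rate.

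**Step 1, closed form without a practice term.** With groups of size m in the Fresh Start arm only, that arm's design effect is DE = 1 + (m − 1)ρ. At 1:1, the correct standard error (SE) of the difference divided by the SE that ignores groups is √((DE + 1) / 2). Example: m = 8, ρ = 0.05 gives DE = 1.35 and √(2.35 / 2) = 1.084.

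| ρ | SE ratio, m = 6 | m = 8 | m = 10 | Coverage of nominal 95%, m = 6 to 10 |
|---|---|---|---|---|
| 0.01 | 1.012 | 1.017 | 1.022 | 94.7% to 94.5% |
| 0.02 | 1.025 | 1.034 | 1.044 | 94.4% to 94.0% |
| 0.05 | 1.061 | 1.084 | 1.107 | 93.5% to 92.3% |
| 0.10 | 1.118 | 1.162 | 1.204 | 92.0% to 89.6% |

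**Step 2, simulation of a linear practice-only mixed model, controls in the same practices.** The ratio is empirical SD over model SE.

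| Set | No group effect | ρ = 0.02 | ρ = 0.05 | ρ = 0.10 |
|---|---|---|---|---|
| Groups of 7-8, 5,000 runs | 0.0793/0.0796 = 1.00; 95.0% | 0.0820/0.0800 = 1.03; 94.6% | 0.0865/0.0805 = 1.07; 92.9% | 0.0924/0.0814 = 1.14; 91.6% |
| Groups of 10, 2,000 runs | not run | 1.07; 94.0% | 1.10; 92.4% | 1.21; 88.9% |
| Third set, 2,500 runs | not given | 1.04; 93.7% | 1.12; 92.2% | 1.19; 90.1% |

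In the 2,000-run set, groups of 6 at ρ = 0.05 gave 1.07 and 93.0%, and the check with no group effect (groups of 8) gave 1.01 and 94.8%. The Monte Carlo error of an SD from 2,000 runs is about 1 / √4,000 = 1.6%, which accounts for part of the spread between sets. As a shortfall in the SE, 1 − 0.0800/0.0820 = 2.4% at the low end and 1 − 1/1.19 = 16% at the high end. With every group at 10 and ρ = 0.10 it is 1 − 1/1.21 = 17%.

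**Step 3, the same model with controls in other practices.** In the 2,000-run set the ratio is 0.98-1.02 with a group effect, and 1.00 (controls in 100 practices) or 1.03 (in 10) without one. In the 2,500-run set it is 1.01-1.04 with a group effect and 1.02 without. A further 4,000-run set, with controls in 100 practices, gave coverage of 93.6% with no group effect, 93.8% at ρ = 0.05 and 93.1% at 0.10. Coverage is slightly below 95% even without groups, so that shortfall is not due to them.

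**Step 4, partial sharing.** With 25% of controls in the same practices and ρ = 0.05, the SE is about 7% too small relative to its no-group baseline.

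**The case against.** The strongest reply is that the size rests on two facts the documents do not supply: the group ICC, and whether controls share practices with Fresh Start patients. WSIC covers 380 practices against an assumed 10 participating ones, and proximity is one propensity-score input, not an exact match on practice. This stands, and it makes the concern conditional. It does not remove it: 1,500 × (1 − 0.20) = 1,200 eligible patients in participating practices would not be enrolled, nothing excludes them as controls, and they share the practice-level deprivation value.

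Sessions also use pre-prepared content, and one nurse may lead every group in a practice, so some of the correlation may sit at practice level. That stands in part: a facilitator effect felt only by treated patients is still not an intercept shared by both arms.

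Thirdly, this is a feasibility study, SAP 7.1.1 calls the primary analyses descriptive, and no decision threshold depends on these intervals. That limits the consequence. SAP 7.5.5 still models the difference in appointments and cost.

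Three stronger readings are not supported:

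- A reader might infer that the intervals are too narrow wherever the controls come from. Step 3 shows otherwise.
- A reader might take SE/SD values of 0.964 and 0.979 at ρ = 0.05 and 0.10, from a 3,000-run simulation with controls in 100 other practices, as a 2-4% shortfall. The no-group value there is already 0.989 and the ordering runs backwards, so this is mostly baseline and noise.
- A reader might infer that appointment counts are the most exposed because a cancelled or moved session affects a whole group. The documents do not say whether a VGC counts as an appointment, moving a session need not change a count, and the Poisson model was not simulated.

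**Conclusion.** The concern holds conditionally. The plan leaves out a level of clustering that its own intervention creates, in one arm only. If controls share practices with Fresh Start patients, an assumed VGC-group ICC of 0.02-0.10 makes the SE of the difference about 2-16% too small and brings coverage of a nominal 95% interval to about 90-95%, and marginally lower if every group has 10 patients. At an ICC of 0.01 the effect is negligible. If controls come only from other practices, it is negligible across the range.

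The figures rest on a linear model, a practice ICC of 0.05 for the outcome, and stable groups. The documents do not say that a patient keeps the same group for all three sessions. The point matters mainly for appointments and cost. For HbA1c, lipids and weight it affects how exploratory intervals are read.

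**What to change.** - Record, for each of the three sessions, the VGC group each patient is booked into and the group attended.
- In the between-group models of SAP 7.5.5 and 7.6.2, add a VGC-group random effect that applies to the Fresh Start arm only (a partially nested model) and keep the practice term.
- Use the first booked group if membership proves largely stable, and a multiple-membership term if it does not. Set the criterion for stability before the comparisons are run.
- Report the practice-only model alongside, and name it as the fallback if the fuller model does not converge.
- Report how many controls come from participating practices, since this decides whether the point matters.

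The cost is a group identifier per session in the study dataset and one model term. The downside is slightly wider intervals and occasional non-convergence. Treatment, visits and eligibility do not change.
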